#### C. Study Design and Research Methods C.1 Study design

The major purpose of this study is to assess the efficacy of CBD on motor symptoms of PD, and secondarily to study the safety and tolerability of CBD and other efficacy, particularly regarding tremor in PD. The study has been powered to detect a clinically significant reduction in MDS UPDRS Part III motor scores. This is a 1:1 parallel, double-blind, randomized controlled trial (RCT) with 60 participants. We will be recruiting up to 75 participants; the goal is to have 60 participants (30 in CBD group and 30 in placebo group) complete the study.

See Appendix 1 Schedule of Events for more detail on study design.

The study drug is obtained from NIDA. How the dose is started and escalated and what target dose is chosen is based on human literature and our open label study, as discussed in Section III under Discussion.

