The study is a randomized, placebo controlled, double-blind parallel design with two treatment arms, each of approximately 2-3 weeks duration. In the 2-3 week treatment phase participants will start study drug and titrate up to the maximum tolerated or targeted dose (2.5 mg/kg/day of CBD). Each participant will have a screening visit, baseline visit within four weeks, 2 dose assessment visits (1.25 mg/kg/day and 2.5 mg/kg/day), and a safety visit (5 visits total). Participants will be evaluated at each dose level for monitoring adverse events, as well as changes in medical history and concomitant medications. Further, in case CBD alters the reliability of self - report, repeated measures will be taken on the third to fifth day at each dose during the clinic visits or at home. The assessments include the assessment of tolerability and symptoms of hepatotoxicity, SCOPA-sleep, Anxiety short form, Depression short form, Emotional and behavioral dyscontrol short form, and EQ-5D-5L. Participants are called 3 and 7 days after stopping the study drug to check for signs of withdrawal. At dose assessment visits, urinary CBD and metabolites will be tested. To maximize compliance the coordinator calls the participant to remind them the next day's clinical visit. To increase compliance with taking study drug, participants will be asked to fill out a diary at home. The diary will be a record of the date and time participants take study drug, dose of the study drug, and adverse and beneficial events. Study drug is dispensed at the baseline visit. Participants will measure their tremor using Tremor GUI MATLAB twice a day (two hours after breakfast dose and two hours after dinner dose) for two consecutive days after screening visit, three consecutive days prior to baseline and each dose assessment visit, as well as during the clinic visits. To evaluate the possible somnolence effect of CBD, participants will be evaluated their alertness before and three hours after they take the study drug at baseline visit.

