# Inclusion and Exclusion criteria:

Inclusion criteria:

- Male or female participants 40 85 years of age.
- Willing and able to give informed consent (including through use of a legally authorized representative (LAR), if necessary).
- Idiopathic PD, per UK Parkinson's Disease Society (UKPDS) Brain Bank Clinical Diagnostic Criteria
- ON motor MDS UPDRS >20.
- Anti-parkinsonian medication is fixed for at least one month prior to the day the participant starts study drug treatment.
- If MoCA<22 participant must have a designated caregiver that agrees to ensure study protocols followed. This includes accompanying patient to study visits and being available for study phone calls.
- Must have a driver or available transportation (including provided Uber vouchers) to drive them to and from study visits and for other transportation needs during the treatment period.
- Has a significant other (someone who knows the participant well) that is appropriate for doing the NPI assessment, and agrees to do so
- Agrees to not take more than 1 gram per day of acetaminophen, due to a possible interaction with study drug that could increase risk of hepatotoxicity.

\*\*Note: the LAR (if required for informed consent), caregiver (required for those with MOCA<22), and significant other (required for all participants) may be the same person in some cases. In other cases, these may be different people.

Exclusion criteria:

- Known or suspected allergy to cannabinoids or excipients used in the study drug formulation.
- Cannabis is detectable at the screening visit by blood testing or at the baseline visit by urine testing. If cannabis is detected at either the screening or baseline visit, then the participant is a screen fail and may return >14 days later for a repeat screening visit. If cannabis is again detected at either the screening or baseline visit, then the participant is excluded and not allowed to rescreen.
- History of drug or alcohol dependence; defined by prior inpatient stay(s) for this or that patient states s/he has a history of this.
- Use of dopamine blockers within 180 days and cocaine, and MAO-A inhibitors within 90 days of baseline.

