- Currently taking tolcapone, valproic acid, felbamate, niacin (nicotinic acid) at ≥2000 mg/day or nicotinamide (nicotinic acid amide or nicotinamide) at ≥3000 mg/day, isoniazid and ketoconazole due to risk of liver injury and clobazam and ketoconazole because of risk of toxic interactions with the study drug. These medications need to be stopped 90 days before the baseline visit.
- Unstable medical condition.
- Any of the following laboratory test results at screening:
  - $\Box$  Hemoglobin < 10 g/dL
  - $\Box$  WBC <3.0 x 10^9/L
  - $\Box$  Neutrophils <1.5 x 10^9/L
  - $\Box$  Lymphocytes < 0.5 x 10^9/L
  - $\Box$  Platelets <100 x 10^9/L
  - $\Box$  Hemoglobin A1C > 9%
- Aspartate aminotransferase (AST) and/or alanine aminotransferase (ALT) > 3 times the upper limit of normal. Persons with stable liver disease of known etiology can be included, unless total bilirubin or prothrombin time/INR is abnormal.
- Is pregnant or lactating, or has a positive pregnancy test result pre-dose.
- If a sexually active female, is not surgically sterile or at least two years post-menopausal, or does not agree to utilize an effective method of contraception from screening through at least four weeks after the completion of study treatment, using one of the following: barrier methods (diaphragm or partner using condoms plus use of spermicidal jelly or foam, preferably double-barrier methods); oral or implanted hormonal contraceptive; intrauterine device (IUD); or vasectomized male partner.
- Planned elective surgery during study participation.

Cytokines testing: Enrolled subjects who meet the following criteria will have blood collected for cytokines test, along with other blood tubes being collected, at screening and at 2.5 mg/kg/day dose assessment visit. If these criteria are not met at screening but are met at baseline visit, the draw for cytokines testing may be done at the baseline visit instead.

- Not currently taking or has not taken in the past 10 days chemotherapeutic or anti-inflammatory medications. A sample of such medications is listed in Appendix A, but it is not possible to list all medications in these broad classes. Thus, the PI will evaluate each subject's medications and decide if any meet this exclusion criteria.

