On site screening visit: Consent, demographics, concomitant medications, family medical history, medical history and physical examination (complete physical exam and detailed neurological exam), vital signs, orthostatic blood pressures, tremor evaluation, MDS-UPDRS III, H&Y rating, MOCA, Drug, alcohol and tobacco abuse screening test, safety assessments (as listed in section IV A, including, QUIP-RS, C-SSRS, NPI, Emotional and behavioral dyscontrol short form, Drug abuse-related AEs), EKG and safety labs (including hematology, hemoglobin A1C, Complete metabolic profile and Liver Function Tests), blood cannabis analysis testing, plasma cytokine level tests, serum pregnancy test (for women childbearing potential), and inclusion/exclusion criteria are done. Study participants are instructed not to take cannabis from outside source throughout the study. Tremor constancy and amplitude measure device (Tremor GUI MATLAB package) is dispatched and participants are instructed to use the Tremor GUI MATLAB package to measure their tremors in the clinic and will perform it independently before they leave the clinic. They will measure the tremors at home twice a day (two hours after breakfast dose and two hours after dinner dose) for two days after screening visit and three days prior to the baseline visit.

To reduce in-person clinic visit time, part of the above procedures can be done remotely after onsite screening visit, including: demographics, concomitant medications, family medical history, medical history, safety assessments (C-SSRS, NPI, emotional and behavioral dyscontrol short form, drug abuse related AEs).

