# C.3 Randomization and drug dispensation:

Patients who consent will be stratified by age (40-60 and 61-80) and disease severity (H&Y 1-2.5, 3-5) and divided into blocks of a few patients each, depending on order of recruitment. Equal numbers from each block will be assigned to CBD or placebo group in random order.

[name], the PI, will obtain an amended DEA Schedule 1 license prior to the shipment of the study drug and all procedures of drug handling will be according to DEA specifications and protocol provided by University of Mississippi researchers. Briefly, designated study personnel will receive the study drug, do the formulation procedure, store it, measure and label it. The PI or PharmDs will dispense to the participant.

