#### Sample Size Justification

Using preliminary data we estimate a standard deviation for the within treatment UPDRS Motor change scores, post treatment compared to baseline, of 6.72, and a correlation between the paired observations of the change score of 0.75. Consistent with the preliminary data we anticipate a mean baseline UPDRS Motor score of 23, so a 25% treatment effect would have a magnitude of 5.75, less than the within treatment mean change score of magnitude 6.10 observed in the preliminary data. The estimated standardized effect size is 0.856. Therefore, the two independent samples T-test, testing for a between treatment difference on the within treatment UPDRS Motor change scores, at alpha = 0.05, would require a total sample size of 46 patients for 80% power, and 60 patients for 90% power. Compensating for the possibility of 20% drop out, we would need to recruit 58 patients for 80% power, and 75 patients for 90% power. Thus we plan to recruit 75 patients with a goal of having at least 60 patients complete the study.

Since other outcomes are either descriptive and/or exploratory, and sample size is limited, adjustment for multiple testing adjustments are not planned across different outcome variables.

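### Does a recruitment figure of 75 that allows for dropout but not for screen failures leave the trial short of 60 completers?

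*Combined protocol and SAP*

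**What the plan says.** Section IV.F, Sample Size Justification, finds that 46 patients in total give 80% power and 60 give 90%, and then inflates: "Compensating for the possibility of 20% drop out, we would need to recruit 58 patients for 80% power, and 75 patients for 90% power". It settles on 75 with at least 60 completing. Section IV.C.1 restates this as a ceiling: "We will be recruiting up to 75 participants; the goal is to have 60 participants".

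Neither place defines the point at which a person counts towards the 75. Elsewhere the vocabulary is loose:

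- Section IV.C.1, on visits: "Each participant will have a screening visit, baseline visit within four weeks".
- The exclusion criteria, on a positive cannabis test: "then the participant is a screen fail and may return >14 days later for a repeat screening visit".
- The cytokine paragraph: "Enrolled subjects who meet the following criteria will have blood collected for cytokines test, along with other blood tubes being collected, at screening".
- Section IV.C.3, on randomisation: "Patients who consent will be stratified by age (40-60 and 61-80".

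The motor-score entry rule is "ON motor MDS UPDRS >20". MDS-UPDRS Part III is rated at the on-site screening visit, where consent is completed; randomisation comes later, at the baseline visit.

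**The concern.** Screen failures are certain to occur: the protocol has a rule for them, and several criteria (motor score, laboratory values, cannabis testing) are checked only after consent. An allowance for dropout alone does not cover them. Because 75 is written as an upper limit, and because people at the screening visit are called participants or enrolled subjects, the 75 can be read as a cap on people consented. Each screen failure would then take a place from a randomised patient. The trial would end with fewer than 60 completers and less than 90% power on its primary endpoint, for a reason that the sample-size section does not mention.

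**Working it through.** **Reproducing the plan's figures.** Inputs from the Sample Size Justification: SD of the change score 6.72; difference 0.25 × 23 = 5.75 points; alpha 0.05; two-sample t-test. Section IV.C.1 gives 1:1 allocation. Sidedness is not stated. A two-sided test reproduces the figures; a one-sided test would give 36 and 50.

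- d = 5.75/6.72 = 0.856.
- 80% power: 22.4 per arm, rounded up to 23, total 46.
- 90% power: 29.7 per arm, rounded up to 30, total 60. Power at 30 per arm is 0.903.
- Inflation N/(1 − 0.20): 46/0.8 = 57.5, so 58; 60/0.8 = 75.

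All four totals match.

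**If 75 are randomised.** 75 × 0.8 = 60 completers, power 90.3%.

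**If 75 are consented.** Completers = 75 × (1 − f) × (1 − dropout), where f is the screen-failure rate. The documents give no f. The pilot baseline table allows rough values, if screened people resemble the pilot:

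- *Lower bound.* Thirteen integer scores with mean 22.92 sum to 298. If all were 21 or more, the excess over 13 × 21 = 273 would be 25. The largest SD arises when one person holds all of it: √[(25² − 25²/13)/12] = 6.93. The reported SD is 9.30, so at least 1 of 13 (8%) scored 20 or less.
- *Normal shape.* P(score ≤ 20) is 0.38 with mean 22.92 and SD 9.30 (all 13), and 0.30 with mean 24.70 and SD 8.93 (the 10 in the efficacy group).
- 20% is an assumed middle value; 10% dropout is an assumed alternative.

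| f | Completers, 20% dropout | Power | Completers, 10% dropout | Power |
|---|---|---|---|---|
| 8% | 55.4 | 88% | 62.3 | 91% |
| 20% | 48.0 | 83% | 54.0 | 87% |
| 30% | 42.0 | 77% | 47.2 | 82% |
| 38% | 37.2 | 72% | 41.9 | 77% |

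With 20% dropout, power falls below 80% once f passes about 25%.

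**Which count does the plan mean?**

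- *Randomisation (Section IV.C.3).* The sentence that begins with patients who consent goes on to form blocks according to the order in which patients are recruited, and assigns equal numbers from each block to the two arms. The recruited are the people who enter the blocks.
- *Dropout (Section IV.F and the participant stopping rules).* Dropout is described as leaving because the study drug is not tolerated, and withdrawals are tabulated by treatment group. A 20% loss of that kind applies to people who have been allocated, so 60/0.8 has randomised patients as its base.
- *Visits (Section IV.C.1).* The five visits of each participant include two on study drug, which a screen failure never has. The sentence describes treated people.
- *Pilot (Section III).* The open-label study is described as having 13 patients, and 13 is the safety group, those who took the drug. The same team's earlier study size counted treated people.

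**The case for a change.** The strongest case for a change is that the wording leans the other way in several places, and the ceiling has no slack to absorb a misreading. A person who fails the cannabis test is still a participant, the same noun as in the ceiling; blood is drawn from enrolled subjects at screening. Dropout is unlikely to supply spare room if the pilot is a guide, since 23% stopped there for intolerability. Interest among patients and a large clinic population (Section IV.E) supply candidates, but do not make them eligible. One sentence of clarification would cost almost nothing.

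Part of this stands: the counting point is undefined, and no number to screen is given. The rest is weaker. Section IV.C.1 also calls this a trial with 60 participants, meaning the target completers, so the noun cannot define the 75. The cytokine paragraph concerns blood sampling, not a recruitment tally. The pilot's 23% arose at much higher doses; applied to 75 randomised it would still leave about 58 completers (75 × 0.77 = 57.75) and 89% power. The 38% rate fits a normal curve to 13 people chosen under a different rule (significant tremor), and assumes that clinicians refer patients without regard to motor severity. The one rate that needs no shape assumption is the 8% minimum. Rescreening after a positive cannabis test would recover some failures. The early termination visit includes efficacy assessments, so some dropouts may still contribute data.

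**Conclusion.** No change follows. The sample-size arithmetic is correct, and on the reading that fits the plan's use of dropout and its randomisation scheme, 75 randomised patients give 60 completers and 90.3% power. A shortfall appears only if the ceiling is applied at consent. It is then about 2 points of power at 8% screen failure and about 8 points at 20%, both with the full 20% dropout; at 8% failure with 10% dropout there is none. The larger losses (77% and 72% power) rest on screen-failure rates of 30% and 38% extrapolated from a small, differently selected pilot.

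What remains is a missing detail. A trial team would ordinarily count the 75 at randomisation, keep a screening log and continue screening until that number is reached. The primary test, the endpoint and the validity of the power calculation do not depend on how many people are consented. This conclusion rests on reading the 75 as randomised patients, which the documents support but do not state.

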#### G. Summarize Knowledge to be Gained:

Marijuana is one of the most used alternative medications. Since it became legal and readily available in Colorado, Parkinson disease (PD) and other movement disorders patients have been trying it, usually without the knowledge of or supervision of their neurologist. This study will promote the safety of our patients and provide data useful in evaluating the effect and safety of CBD on tremor, cognition, anxiety, psychosis, and other symptoms, including sleep, impulsivity, suicidality, mood, fatigue, restless legs syndrome, pain, bradykinesia, rigidity, balance, and dyskinesia in PD patients. Data from this study are essential to aid in designing future marijuana research.

Vital Signs (c)	$\checkmark$	$\sqrt{(n)}$	$\mathbf{N}$	√(p)			$\checkmark$
			(n)				,
Orthostatic Blood Pressures	$\checkmark$	$\sqrt{(n)}$	$\mathbf{N}$	√(p)			$\checkmark$
check	,		(n)				
Height and Weight							
Complete Physical Exam (d)							
Neurological exam (e)			$\checkmark$	$\checkmark$			
Brief physical exam (heart							
and lung auscultation)							
Hematology (f)							
							(m)
Hemoglobin A1C	$\checkmark$						
Complete metabolic profile +							
LFTs (g)							(m)
Plasma cytokines test							
Blood cannabis analysis			1	√ (o)			
			(0)	. (-)			
Urinalysis (h)			$\sqrt{1-1}$				
	,						(m)
Urine drug (THC) test							()
Urinary CBD and					1		 
metabolites levels test (q)							
Urine cups dispense and					1		
urine collection instruction							
	I I				1	1	

ECG (12-LEAD)	$\checkmark$		$\checkmark$		$\checkmark$	
Serum Pregnancy Test (for women childbearing potential)	$\overline{\mathbf{v}}$					(m)
Urine Pregnancy Test (for women childbearing potential)			N			
Assessment of past marijuana use	√					
Drug, alcohol and tobacco abuse screening test	√					
MOCA	$\checkmark$					
Cognitive assessment battery						
Alertness test (Stanford Sleepiness Scale SSS)		$\sqrt{(t)}$ (y)				
MDS-UPDRS part III	$\checkmark$					
MDS-UPDRS (all 4 parts)						
H & Y rating	$\checkmark$					
Schwab & England Daily Activities Scale	$\checkmark$				$\checkmark$	
TUG						
QUIP-RS	$\checkmark$		$\checkmark$			
C-SSRS	$\sqrt{(r)}$	$\sqrt{y}$	$\checkmark$			$\sqrt{(z)}$
RBDSQ		$\sqrt{(y)}$				$\sqrt{(z)}$
NPI	$\sqrt{(\mathbf{r})}$		$\checkmark$		$\checkmark$	$\sqrt{(z)}$
Anxiety short form		√(y)	$\checkmark$		$\checkmark$	$\sqrt{(z)}$
Depression short form		√(y)			$\checkmark$	$\sqrt{(z)}$
Emotional and behavioral dyscontrol short form	√( r)		$\checkmark$	√		$\sqrt{(z)}$
SCOPA-sleep		√(y)		$\checkmark$		$\sqrt{(z)}$
IRLS		$\sqrt{(y)}$				$\sqrt{(z)}$

Fatigue severity scale			√(y)						$\sqrt{z}$
Pain intensity and interference short form			√(y)	$\checkmark$			$\checkmark$		$\sqrt{z}$
Bladder function-OABSS			$\sqrt{y}$	$\checkmark$			$\checkmark$		$\sqrt{z}$
PDQ-39			$\sqrt{y}$				$\checkmark$		$\sqrt{z}$
EQ-5D			$\sqrt{y}$						$\sqrt{(z)}$
CGI							$\checkmark$		
PGI-I									
PGI-C									
Unified Dyskinesia Rating Scale (UDysRS)							$\checkmark$		
NMSS			$\sqrt{y}$				$\checkmark$		$\sqrt{(z)}$
Dermatology Intake Form			$\sqrt{(y)}$						
DLQI			$\sqrt{(y)}$				$\checkmark$		
Insomnia Severity Index (ISI)			$\sqrt{(y)}$				$\checkmark$		
Modified Dysfunctional Beliefs and Attitudes about Sleep Questionnaire (DBAS- 16)			√(y)	$\checkmark$			V		
Pittsburgh Sleep Quality Index			√(y)	$\checkmark$			$\checkmark$		
Home diary dispense & instruction									
Home diary collection & review				$\checkmark$			$\checkmark$		
Tremor constancy and amplitude measure (k)				$\checkmark$	$\checkmark$		$\checkmark$		
Tremor measure device dispatched and instruction	$\checkmark$								
PSG equipment set up and instruction		$\sqrt{\mathbf{x}}$				$\sqrt{(u)}$			

Patient Instruction sheet for	$\sqrt{\mathbf{x}}$						√ (u)					
At-Home Sleep Monitoring	. ()						. ()					
Test dispense												
Morning Daytime	$\checkmark$											
Dysfunction Questionnaire												
(v)												
Sleep Diary (v)												
PSG equipment and data								$\checkmark$				
collected (w)												
skin evaluation (photo of		$\checkmark$						$\checkmark$				
central face)												
* Questionnaire reminder phot												
Note: regarding the rows of da	,		,									
a. A complete medical history												
at the Screening Visit and reco							ther enro	llment o	riteria	will t	be review	red and
updated at the Baseline/Day 1												144
b. Adverse events will be reco				-				Any sub	ject wi	th an	ongoing	AE will
be followed until the AE is res						nvesti	gator.					
c. Vital signs obtained after the	2	U					1 1		••	1	• •	
d. Complete PE to include: ski	n, head-neck, ey	yes-ears-nos	se-throat,	ungs-ch	est, he	eart, a	bdomen	, extrem	ities, n	eurol	ogical.	
e. Neurological exam.												
f. Hematology consists of hem												
(MCHC), red blood cell count												
g. Serum chemistry (fasting no												
chloride, creatinine (MDRD fo					orato	ry), g	lucose, p	otassiui	n, alan	ine ai	minotrans	sierase,
aspartate aminotransferase, so					atomer			ita 11	ا مسرد ا			
h. Urinalysis dipsticks includin	• •										•	
bilirubin. If nitrite, blood, or particular to remind them to			neroscopi	C CXaiiiii	iation	WIII	be perior	meu al		uai la	aboratory	•
			fairmant	with dans	ro1							
j. Call patient to collect advers	e events and inf	ormation of	signs of	withdraw	/al							

k. Tremor time percentage and amplitude will be measured by a portable device and laptop. Subject will measure it at home 2 days after screening visit, 3 days before baseline visit, 3 days prior to each dose assessment visit, twice a day (2 hours after breakfast dose and 2 hours after dinner dose), 90 seconds each measurement. Tremor will also be measured at clinic, twice at screening visit, 2 hours after taking study drug at baseline and each dose assessment visit.

1. Treatment assessment visit can occur on 10 (+4) days for each dose.

m. Hematology, chemistry, urinalysis and EKG will be done if there was a clinically significant change at the high dose evaluation visit compared to baseline visit.

n. Subject will be monitored and vital signs will be checked again at before and 1 hour after taking the study drug.

o. Blood drawn will be performed 3 hours after taking the study drug of the clinical visit day.

p. Subject will be monitored and vital signs will be checked at before and 1 and 3 hours after taking the study drug.

q. Clean catch urine collection after taking the study drug. Urine is collected in a 500 mL container and stored in 3-4 small cups (120 mL, fill up to 3/4).

r. Procedures can be done remotely after onsite screening visit

s. Phone call to remind patient to measure tremors at home for consecutive 3 days before the next clinic visit.

t. Alertness test will be done before and 3 hours after taking study drug.

u. Home sleep test will be done after at least 7 days on the max dose and until (including) the 3rd night before 2.5 mg/kg/day dose assessment visit.

v. Morning Daytime Dysfunction Questionnaire and Sleep diary will be done within the first 30 minutes of waking after home sleep test.

w. PSG equipment and data collected on the next day of home sleep test or at baseline or 2.5 mg/kg/day dose assessment visit

x. The sleep study before the baseline visit is to be done from 14 to 3 nights before baseline visit.

y. Procedures can be done remotely, between screening and onsite baseline visit

z. procedures can be done remotely 1-3 days prior to or after safety follow up visit

